4.5 Early Termination

Participation in the study is completely voluntary and a subject can choose to withdraw from the study at any time. In addition, a subject can be withdrawn for any of the following reasons: the Principal Investigator decides that continuing the drug may have an increased or unforeseen risk to the subject, a subject is non-compliant with the protocol, a subject has a serious reaction to the treatment, or the study is stopped by the Independent Ethics Committee, US Food and Drug Administration (FDA), or Zosano Pharma.

In order to complete all treatments for each dose, additional subjects may be enrolled to account for subjects who withdraw or are discontinued from the study. If a subject does not complete all planned treatments, the reason and date of withdrawal from the study must be recorded in the CRF. Zosano Pharma should be notified immediately if a subject withdraws prematurely from the study.

5 STUDY TREATMENTS

5.1 Study Drug Treatments

The treatments are:

- Treatment A: M207 3.8 mg administered as two 1.9 mg patches 30 min wear time (upper arm application) - made on a “Sled” coater and packaged in foil pouches
- Treatment B: M207 3.8 mg administered as two 1.9 mg patches 30 min wear time (upper arm application) - made on a “MACAP” coater and packaged in foil cups
- Treatment C: M207 3.8 mg administered as two 1.9 mg patches 30 min wear time (upper arm application) - made on a “MiniMac” coater and packaged in foil cups
- Treatment D: zolmitriptan nasal 2.5 mg/0.1 ml (single dose)

Depending on the treatment assignment, two M207 patches will be applied to the upper arm by means of a handheld reusable applicator with an application energy of 0.26 Joules. Used patches will be removed 30 minutes after application of the second patch. The patches will be collected and frozen in storage until shipped for analysis of remaining drug.

The applicator systems and unused patches should be stored at room temperature, not to exceed 15-30°C (59-86°F). Unused patches should not be refrigerated or frozen.

5.2 Study Treatment Assignment and Schedule

The 24 subjects are planned to receive each of the four treatments (A, B, C, D) 48 hours apart. Subjects will be randomly assigned to one of 4 treatment sequences.

At the end of each dosing day, the safety data from the subjects will be evaluated. If tolerability is deemed to be acceptable by the Principal Investigator, a decision will be made to proceed to the next dosing day.

5.3 Study Treatment Accountability Procedures

All transdermal M207 Patch System components are to be used only in accordance with this protocol under the supervision of the Investigator. The Investigator will maintain detailed and verifiable records that document the receipt, storage, dispensing, and return of all M207 Patch System components provided by Zosano Pharma. These records will include a listing of which study drug supplies were dispensed for particular subjects treated in the study, by whom, when, and the specific quantities dispensed and remaining at the completion of the subject's investigational treatment. Reasons for departure from the expected dispensing and dosing regimen will also be documented. All left over used and unused study patches should be retained for drug accountability auditing to be performed by Zosano Pharma or its representatives. At the conclusion of the study, the study drug accountability records must accurately reflect the receipt and final disposition of all study drug shipped to the site. Destruction or return of remaining used and unused drug supplies by the study site will occur only upon receipt of written authorization by Zosano Pharma or its representatives.

5.4 Prior and Concomitant Medications Allowed and Prohibited During the Study

Subjects will be asked to refrain from taking either prescription or OTC (inclusive of herbal) medications within one week prior to dosing until the completion of the study, except for those discussed in this section. All concomitant medications taken during the study will be recorded on the concomitant medications case report form (CRF) with indication for use, totally daily dosage, and dates of drug administration.

Allowed prescription and over the counter medications:

- Hormone Replacement Therapy (HRT)
- Birth control pills, patches, IUD, rings, injections, or implants (all hormonal contraceptives) are allowed provided the dose has been stable for at least three months prior to screening and may be continued throughout the study
- Proton Pump Inhibitors (PPIs)
- Intermittently used NSAIDS
- Acetaminophen may be administered if medically necessary (not more than 1000mg/day)
- Antihistamines

All other concomitant medications will be prohibited, except as specifically exempted by the Sponsor on a case-by-case basis.

6 STUDY VISIT SCHEDULE AND GENERAL CONSIDERATIONS

Following review of all Screening procedures, eligible subjects will be enrolled into the dosing phase of the study. The interval between screening and first treatment may be up to 30 days. Eligible subjects will be admitted into the clinic on the day before the first dosing. The washout period following each dose must be a minimum of 48 hours (from time 0 = application of patches) until the next dose. Subjects will be required to stay in the clinic for the entire duration of the study (unless medically necessary to leave the clinic as instructed by the principal investigator and/or for non-medically related reasons considered on a case by case basis).

The PK samples should be drawn as close as possible to the specified time. When multiple procedures are scheduled for the same time point, PK samples will be taken at the protocol assigned time point within plus or minus 1 minute of the specified time points for the first hour and within plus or minus 5 minutes of the specified time points after one hour. The other measurements (i.e., vital signs, ECG, skin assessments) will be taken before or after the protocol-specified time point within an interval of plus or minus 5 minutes.

Subjects will refrain from smoking or using tobacco products during the clinic stay. Standardized meals and beverages will be served the evening prior to dosing and will be provided by the clinical site. Water is allowed ad libitum, as well as tea and coffee in moderate amounts. Breakfast can be served approximately two hours post-dosing, lunch approximately 4-6 hours after dosing, the last evening meal of the day will be served approximately 8-10 hours post dosing, and an evening snack is permitted no later than 13 hours post dose. The evening prior to dosing, subjects will fast overnight and receive only clear liquids.

Alcohol is prohibited 24 hours before study drug administration until discharge from the clinic.

Subject will not engage in any activity that may cause inflammation, irritation, sunburn, lesions or tattoos at the intended application sites from two weeks prior to screening through their last day of study participation.

Subjects will not engage in strenuous activity at any time during their stay at the clinical unit.

No lotions, ointments, or powders may be applied to the upper arm where M207 will be applied for 12 hours before or after applying M207.

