4 INVESTIGATIONAL PLAN

4.1 Overall Study Design

This is a single-center, open-label, randomized, four-way crossover study. Each subject will receive each of the four study treatments once, followed by in-clinic monitoring and extensive blood sample collection for pharmacokinetic analysis.

Dosing will occur approximately 48 hours apart from the time of patch application, until completion of dosing in randomized order per the treatment sequence schedule. Plasma samples from the dosing days will be sent to the analytical laboratory for analysis and tolerability for each of the dose levels will be summarized.

After completion of the four dosing days, subjects will be assessed one final time and dismissed from the study.

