6.3 Study Dosing Days

General Considerations

Subjects will fast for at least 10 hours during the night preceding dosing and until at least 2 hours after dosing. Water is allowed ad libitum, as well as tea and coffee in moderate amounts. The following morning (between 0630 and 0930), subjects will receive that day's scheduled treatment (A, B, C or D). Breakfast should be withheld until at least two hours post patch application.

No lotions, ointments, or powders may be applied to the upper arm where M207 will be applied for 12 hours before or after applying M207.

All AEs, including any skin irritations and sensations as well as concomitant medication usage will be documented.

When multiple assessments are required at the same time point, they will be conducted in the order as specified in the footnotes of the Schedule of Assessment. All procedures should be performed relative to "Time 0" (M207 application) when a time is listed.

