11.4 Monitoring

The clinical site will permit trial-related monitoring, audits, IRB review and regulatory inspections by providing direct access to source data/documentation.

The sponsor's representatives will monitor the study at all stages of study conduct from inception to completion in accordance with current GCPs/ICH-R and a study monitoring plan. This monitoring will be in the form of site visits and other communication and will include review of original source documents and CRF. The sponsor's monitor or representative will notify the principal Investigator prior to conducting any investigational site visit. The frequency of these visits will depend upon the progress of the study, and will include monitoring to assess facilities,

and required certifications, IRB notifications and approvals, equipment, recruiting, record-keeping, protocol adherence, data collection, adverse event reporting and other factors.

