13 SCHEDULE OF ASSESSMENTS

Assessment*	Screening Visit**	Admission/ baseline	Dosing Visit***																End of Study/Early Termination
			Pre-dose	0 mn	2 mn	5 mn	10 mn	15 mn	20 mn	30 mn	45 mn	60 mn	90 mn	2 hr	4 hr	8 hr	12 hr	24 hr	
	Screening	Day Prior to first Dose																	Approximately 48 hours after completion of all procedures on final dosing day
Informed consent	X																		
Medical history/ demographics	X																		
Concomitant medications																			→
Physical exam	X																X		X
Serum pregnancy test	X	X																	X
Height	X																		
Weight	X																		X
Confirm eligibility	X	X	X																
Clinical laboratory tests chemistry, hematology, UA)	X																		X
Serology	X																		
Urine Drug & Alcohol Testing	X	X																	
Collect PK samples			X	X	X	X	X	X	X	X	X	X	X	X	X	X	X	X	
Study drug administration				X															
Vital signs (inclusive of temperature at screening, admission, and end of study/or ET only)	X	X	X				X					X		X	X		X		X
ECG	X		X					X									X		X
Remove and retain (freeze) patches											X								

Assessment*	Screening Visit**	Admission/baseline	Dosing Visit***																End of Study/Early Termination
			Pre-dose	0 mn	2 mn	5 mn	10 mn	15 mn	20 mn	30 mn	45 mn	60 mn	90 mn	2 hr	4 hr	8 hr	12 hr	24 hr	
	Screening	Day Prior to first Dose																	Approximately 48 hours after completion of all procedures on final dosing day
Nasal Assessment for Treatment D only			X																
Investigator skin assessment of the application sites ****			X								X		X			X	X	X	
Swabbing										X									
Record Adverse events																			→

* When multiple procedures are scheduled for the same time point, PK samples will be taken at the protocol assigned time point within plus or minus 1 minute of the specified time points for the first hour and within plus or minus 5 minutes of the specified time points after one hour. The other measurements (i.e., vital signs, ECG, skin assessments) will be taken before or after the protocol-specified time point within an interval of plus or minus 5 minutes.

** Screening Visit – Up to 30 days prior to the Admission/Baseline visit.

*** The washout period following each dose must be a minimum of 48 hours post removal of the second patch (in each treatment A, B, and C dosing period) until the next dose is administered.

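### Does the 30-minute gap between the two stated washout minimums require a change to the plan?

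*Protocol*

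**What the plan says.** The protocol describes the gap between doses in four places.

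- **Section 6** (visit schedule) sets a floor counted from application: "The washout period following each dose must be a minimum of 48 hours (from time 0 = application of patches) until the next dose".
- **Section 13** (Schedule of Assessments, footnote marked with three asterisks) sets a floor counted from removal; it "must be a minimum of 48 hours post removal of the second patch (in each treatment A, B, and C dosing period").
- **Section 4.1** gives the general design: "Dosing will occur approximately 48 hours apart from the time of patch application".
- **Section 5.2** gives the plan: "The 24 subjects are planned to receive each of the four treatments (A, B, C, D) 48 hours apart".

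Three further statements bear on the comparison. Section 6.3.1.2 defines time 0 as application of the second patch. Section 5.1 fixes the wear time: "Used patches will be removed 30 minutes after application of the second patch". Section 6.3 confines dosing to a clock window: "The following morning (between 0630 and 0930), subjects will receive" the scheduled treatment.

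**The concern.** Section 6 and the Section 13 footnote are both worded as mandatory minimums for the same interval, yet they start counting at different events. A site that doses at exactly the spacing named in Section 5.2 would comply with Section 6 and fall short of the footnote after every M207 dose that has another dose behind it.

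The consequence would be inconsistent deviation records. Section 5.3 says "Reasons for departure from the expected dispensing and dosing regimen will also be documented", and the monitoring described in Section 11.4 covers "protocol adherence, data collection, adverse event reporting and other factors". Two people applying different passages could label the same interval differently. In a crossover trial, any doubt about washout also raises the question of carryover, which could bias the comparisons between formulations and with the nasal spray. Finally, a longer floor pushes doses later in the day, against a fixed morning window.

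**Working it through.** **1. Common time scale.** Inputs: 48 h (Sections 6 and 13), removal 0.5 h after the second patch (Section 5.1), time 0 at the second patch (Section 6.3.1.2).

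- Section 6 floor: 48.0 h from time 0.
- Footnote floor after A, B or C: 0.5 + 48.0 = 48.5 h from time 0.
- Difference: 0.5 h, or 0.5/48 = 1.0% of the interval.

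Reading time 0 as the first patch would widen the gap slightly, so that reading does not remove the conflict. The footnote sets no minimum after D.

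**2. Can both be met?** Both are lower limits and neither has an upper limit. After M207:

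| Interval from time 0 | Section 6 | Section 13 footnote |
|---|---|---|
| 48.0 to under 48.5 h | met | not met |
| 48.5 h or more | met | met |

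No instruction forces a site to break either rule.

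**3. How many intervals could be labelled two ways?** Each completer has three intervals. If D is last, all 3 follow an M207 dose; otherwise 2 of 3 do. For 24 completers there are 24 × 3 = 72 intervals:

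- D never last: 24 × 2 = 48.
- D always last: 24 × 3 = 72.

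These counts require every relevant interval to fall below 48.5 h. They are conditional upper figures, not expected deviations.

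**4. Does the dosing window bind?** Suppose every interval is held at its bare minimum under the footnote, with 48 h after D:

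- D last: 3 × 48.5 = 145.5 h, against 3 × 48 = 144 h, so dose 4 is 1.5 h later in the day than dose 1.
- D not last: 2 × 48.5 + 48 = 145.0 h, so 1.0 h later.

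The window from 0630 to 0930 is 3 h wide, so the drift fits if dose 1 is given by 0930 − 1.5 h = 0800, or 0930 − 1.0 h = 0830. Lengthening any one interval removes even this limit. The stay has room for that. One day from admission, 145.5/24 = 6.1 days of dosing, one day of sampling after the last dose and two days to the final visit make 1 + 6.1 + 1 + 2 = 10.1 days. The Synopsis allows about two weeks.

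**5. Does 30 minutes matter for carryover?** The protocol gives no half-life. As an assumption, take first-order elimination with a half-life of 2 to 4 h. Fraction remaining = 0.5^(t / half-life).

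| Assumed half-life | At 48.0 h | At 48.5 h |
|---|---|---|
| 2 h | 5.96e-8 | 5.01e-8 |
| 3 h | 1.53e-5 | 1.36e-5 |
| 4 h | 2.44e-4 | 2.24e-4 |

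In the least favourable row, 0.024% remains against 0.022%. The pre-dose sample required in every period (Section 6.3.1.1) also allows residual drug to be seen directly.

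**6. What depends on the washout anchor?** The pharmacokinetic sampling times and parameters (Sections 4.2 and 10.4) run from administration within each period, and the safety changes run from that period's pre-dose value. None uses the interval between doses. No sample size, power or error-rate figure depends on it either; Section 10.1 states that no formal calculation was made.

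**The case for a change.** The best case for acting is that both statements are current, legible and mandatory, and that Section 5.2 names a spacing which, taken literally, misses the footnote. The word approximately in Section 4.1 describes a plan and does not soften a floor stated elsewhere. Dosing intervals belong in the protocol and are not something a statistical analysis plan would settle. The correction would cost a few words.

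Most of this stands as description. The anchors do differ, and an interval just over 48 h is compliant or not depending on the page consulted. The weight placed on it does not hold up:

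- Section 5.2 gives a nominal plan, without an exact interval or an upper limit.
- The Section 5.3 sentence comes from drug accountability, and adherence is one item in a general monitoring list in Section 11.4. Neither shows that the half hour would alter a decision or a result.
- The reference event for D is largely clear. Section 6 applies to each dose, and Section 6.3.1.2 places nasal administration at the same time-0 step as patch application.

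**Conclusion.** The inconsistency is genuine and is worth 30 minutes: 48.0 h against 48.5 h from time 0 after A, B or C. The passages in Section 6 and the Section 13 footnote must be reconciled to one reference event, which is for the sponsor to choose; this review takes no view on which is right. That is an editorial clarification of the kind Section 11.1 classes as administrative. Its only consequence is how intervals in a half-hour band are labelled.

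No change to the design, data collection or analysis follows, because none would alter an estimate, its precision or a conclusion. The arithmetic on the two floors rests on the protocol's own figures. The statement that carryover is negligible rests on the assumed half-life of 2 to 4 h.

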6.1 Screening

All Screening procedures will be performed after obtaining informed consent and should be completed within 30 days prior to admission for the first of four sequential treatments within the study. The screening procedures include:

6.1.1 Screening Visit (Up to 30 days prior to the Admission/Baseline Visit)

Subjects who are considered to be good candidates for the study will be seen in the clinic and have the following procedures performed:

- Obtain informed consent

- Obtain a medical history and demographics
- Record concomitant medications
- Perform a physical examination
- Measure Vital signs (inclusive of temperature)
- Measure height
- Measure body weight and calculate BMI
- Confirm eligibility
- Collect blood and urine samples for clinical laboratory tests
- Perform serum pregnancy test (for all females)
- Collect blood for serology (HIV, Hepatitis B, Hepatitis C)
- Perform urine drug and alcohol testing
- Record a 12-lead ECG

Medical history, physical examination, ECG and laboratory findings are to be reviewed, and eligibility determined. The sponsor must approve any exception to the inclusion or exclusion criteria before planned admission for dosing.

A subject number will be assigned when the subject signs the informed consent. Only subject number, initials and date of birth will identify subjects to the Sponsor. In the event that a subject who has signed the informed consent but did not receive a dose of study medication experiences an SAE, the following information will be captured: demographic data (initials, age, and race), all other Screening assessments that have been completed, AE(s), and concomitant medication(s).

6.2 Admission/Baseline Visit (Day Before the first Dose)

If subjects continue to meet all entry criteria on the day prior to the first dosing, the subject will stay in the clinic overnight and through the final discharge. The following procedures will be performed the day prior to the first dosing only:

- Record concomitant medications
- Perform urine drug and alcohol testing
- Serum pregnancy test (all women)
- Collect vital signs (inclusive of temperature)
- Confirm eligibility

6.3 Study Dosing Days

General Considerations

Subjects will fast for at least 10 hours during the night preceding dosing and until at least 2 hours after dosing. Water is allowed ad libitum, as well as tea and coffee in moderate amounts. The following morning (between 0630 and 0930), subjects will receive that day's scheduled treatment (A, B, C or D). Breakfast should be withheld until at least two hours post patch application.

No lotions, ointments, or powders may be applied to the upper arm where M207 will be applied for 12 hours before or after applying M207.

All AEs, including any skin irritations and sensations as well as concomitant medication usage will be documented.

When multiple assessments are required at the same time point, they will be conducted in the order as specified in the footnotes of the Schedule of Assessment. All procedures should be performed relative to "Time 0" (M207 application) when a time is listed.

6.3.1 Dosing Visit (all Periods) – All Treatments

The following procedures will be performed on each of the four dosing days. The actual procedures will be identical at each of the dosing days, only the study drug administered on each of the treatment days will vary.

6.3.1.1 Pre-Dose - Before treatment Administration on the Day of Dosing

- Record concomitant medications
- Confirm eligibility
- Measure vital signs
- Record a 12-Lead ECG
- Investigator visual skin assessment
- Nasal assessment (visual inspection) for treatment D assignment only
- Determine that subject is stable and in good health and appropriate for dosing
- Collect blood for a PK sample within 15 minutes prior to administering study drug

6.3.1.2 Treatment Administration (time 0 is application of second patch)

- Apply patches or administer intranasal zolmitriptan (see [Appendix 1](#) for instructions on patch administration)
- Begin recording all AEs, whether observed by investigator, reported by the subject, observed in laboratory findings, or discovered by other means, on the AE CRF through the End of Study (or Early Termination) final visit. All adverse events must be followed to resolution.

6.3.1.3 2 Minutes after Treatment Administration

- Collect blood for a PK sample
- Record concomitant medications

6.3.1.4 5 Minutes after Treatment Administration

- Collect blood for a PK sample
- Record concomitant medications

6.3.1.5 10 Minutes after Treatment Administration

- Collect blood for a PK sample
- Measure vital signs
- Record concomitant medications

6.3.1.6 15 Minutes after Treatment Administration

- Collect blood for a PK sample
- Record a 12-Lead ECG
- Record concomitant medications

6.3.1.7 20 Minutes after Treatment Administration

- Collect blood for a PK Sample
- Record concomitant medications

6.3.1.8 30 Minutes after Treatment Administration

- Collect blood for a PK sample following removal of the second patch
- Record concomitant medications and adverse events
- Remove patches and perform the following procedures in the order listed below:
 - Investigator visual skin assessment of the patch application sites within one minute of removing both patches and prior to swabbing
 - Retain and package patches for freezing. Refer to full instructions in [Appendix 3](#).

- Application site swabbing. Refer to full instructions in [Appendix 3](#).

6.3.1.9 45 Minutes after Treatment Administration

- Collect blood for a PK sample
- Record concomitant medications

6.3.1.10 60 Minutes after Treatment Administration

- Collect blood for a PK sample
- Measure vital signs
- Record concomitant medications and adverse events

6.3.1.11 90 Minutes after Treatment Administration

- Collect blood for a PK sample
- Record concomitant medications

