STUDY DURATION	Screening (up to 30 days prior to dosing); in-clinic duration of study participation for each subject is approximately 2 weeks total (includes 4 treatment periods), and the End of Study (or Early Termination) visit occurs on the day of discharge
PROCEDURES & ASSESSMENTS	
All procedures are performed relative to Time 0 (M207 application), the time of second patch application.
 
• Physical examination (Screening, 8 hr post drug administration and End of Study/or Early Termination visit)• Clinical laboratory tests (Screening, and End of Study/or Early Termination visit)• Collection of blood samples (pre-dose, 2, 5, 10, 15, 20, 30, 45, 60, 90 min, 2 hr, 4 hr, 8 hr, 12 hr and 24 hr post-dose) for pharmacokinetics determination• Vital signs (Screening, pre-dose and 10 min, 60 min, 2 hr, 4 hr, 12 hr post-dose and End of study/or Early Termination visit)• 12-lead ECGs (Screening, pre-dose, 15 min, 12 hr post-dose, and End of Study/or Early Termination visit)• Investigator visual skin assessment of the M207 application site at pre-dose, 30 min, 60 min, 8 hr, 24 hr post-dose, and End of Study/or Early termination visit• Residual zolmitriptan swabbing on the skin at 30 min post-dose

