7.3.7 Recording Adverse Events

Adverse events are collected from the time of first patch application until the end of the study (discharge from the clinic). A detailed discussion regarding the collection and reporting of adverse events is provided in [Section 8](#).

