9 DATA MANAGEMENT

9.1 Data Collection

Designated investigator staff must enter the information required by the protocol into the study CRF on an ongoing basis. The completed CRF pages will be reviewed against source documents by the monitor at each monitoring visit. If any data, signatures, or forms are missing or incorrect, the Investigator will be informed and corrections made. Celerion standard CRFs will be supplied. CRFs are produced, stored electronically, and are available to the designated study team members. Each CRF is reviewed and signed by the PI. The final signed CRFs are provided to the Sponsor on CD.

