2. Attach the patch and ring to the applicator by placing the applicator directly on top of the patch ring and push down gently until the patch clicks into place. You will likely hear or feel a "click." The patch is now attached to the applicator.
3. Holding the bottom half of the applicator with one hand, unlock the applicator by twisting the top half of the applicator clockwise until it clicks into the "2" position.
The patch and applicator are now ready for application.
4. Ensure the number shows '2' in the window, indicating the applicator is unlocked. If not, go back to step 4 to change it from '1' to '2'.
5. Place the applicator on the skin and push the applicator against the skin.
6. When you have pushed against the skin hard enough, you will hear the plunger push the patch from the ring onto the skin. Continue to hold the applicator down against the skin for 3 seconds. The patch is now applied and the medicine is now being delivered through the patch. You may now remove the applicator. You will see the patch sticking to the skin. The empty plastic ring will still be attached to the applicator.
7. If edges of the patch are lifted or curled, lightly press down **WITH THE FLAT OF YOUR PALM** to make the patch stick to the skin better.
8. **DO NOT USE YOUR FINGERTIPS** to press the edges of the patch because your fingertips may push one side down but pull the other side loose.
9. With your forefinger and thumb, remove the ring from the bottom of the applicator by pulling it out. You may discard the ring in the rubbish bin.
10. Leave the patches on the subject's skin for the duration assigned in accordance with the protocol treatment assignment (30 minutes).

Figure 1: M207 Patch Application

	
3. Place applicator against cleaned area and press applicator downward to apply patch to skin until you hear a click then HOLD for 3 seconds. Patch is applied. Ring assembly remains attached to the applicator

	
4. Remove the outer ring in order to load and apply the second patch.

	
5. Repeat all of the above steps to apply second patch next to the first patch

4. After Applying the Patch

Leave the patches on the subject's skin for the duration assigned in accordance with the protocol.

Before applying the second patch, remove the used plastic support ring from the applicator and discard it. Use your finger to pull the used patch ring off the applicator. Throw away the patch ring.

5. Removing the Patch

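### Does starting the M207 clock at the second patch, without requiring the first-patch time, spoil the early comparison with the nasal spray?

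*Protocol*

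**What the plan says.** The dosing-visit instructions define the origin in the heading of section 6.3.1.2: "Treatment Administration (time 0 is application of second patch". The Synopsis (Procedures & Assessments) says the same: "All procedures are performed relative to Time 0 (M207 application), the time of second patch application". Section 5.1 ties removal to the same event: "Used patches will be removed 30 minutes after application of the second patch". The first patch is therefore worn for 30 minutes plus the interval between the two applications.

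Appendix 1 describes the applications as sequential. Once a patch has been pressed on, "The patch is now applied and the medicine is now being delivered through the patch". After the ring is removed the instruction is "Repeat all of the above steps to apply second patch next to the first patch". No target or maximum interval is given.

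On records:

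- Appendix 2 requires the actual date and time of each blood draw.
- Section 5.3 requires records showing "which study drug supplies were dispensed for particular subjects treated in the study, by whom, when", which is a dispensing record and not a per-patch application time.
- Section 9.1 says "Celerion standard CRFs will be supplied"; the form itself is not part of the protocol.
- Section 7.3.7 starts safety collection earlier than the PK clock: "Adverse events are collected from the time of first patch application until the end of the study".

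Two places use shorter wording. Section 6 counts washout from the application of patches, and section 10.4 counts Tmax from study drug administration. Neither says which patch.

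**The concern.** Comparing the three M207 treatments with intranasal zolmitriptan is the second study objective (section 2), and the endpoints in section 4.2 include Tmax and AUC0-30min. Treatment D is one spray at time 0. For A, B and C, half the dose goes on before time 0. A clock that starts after dosing has begun shortens the apparent Tmax and can lift the earliest concentrations, and at first sight both favour M207.

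The apparent remedy is to measure the interval and show its effect. That needs the first-patch clock time, which the protocol does not expressly ask for. A statistical analysis plan can choose between clocks, but it cannot recover a time that nobody wrote down. If the head start were large, the early comparison with the spray could be misread.

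**Working it through.** **Inputs from the protocol.** Each patch carries 1.9 / 3.8 = 50% of the dose (section 5.1). Post-dose draws are at 2, 5, 10, 15, 20, 30, 45, 60 and 90 min and 2, 4, 8, 12 and 24 h (Synopsis). AUCs use the linear trapezoid (section 10.4). Draw windows are ±1 min in the first hour (section 6).

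**Assumed, because the protocol gives neither gap nor kinetics.** Inter-patch gap g of 1, 2 or 5 min; one compartment with first-order absorption; single-patch Tmax of 10, 15, 20 or 30 min and half-life of 90 or 180 min (8 scenarios).

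**Formulae.**

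- Unit-dose profile: c(t) = [ka/(ka − ke)] × (exp(−ke·t) − exp(−ka·t)), with ke = ln 2 / half-life and ka solving ln(ka/ke)/(ka − ke) = Tmax.
- Second-patch clock: 0.5·c(s) + 0.5·c(s + g) at each sampling time s, with the pre-dose value of 0 placed at time 0.
- First-patch clock: the same concentrations placed at s + g, interpolated linearly at 30 min.
- Reference: c(s), both patches applied at once.

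**One case in full.** Tmax 20 min, half-life 90 min, g = 2 min, giving ke = 0.00770 and ka = 0.159 per min.

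| Time (min) | 0 | 2 | 5 | 10 | 15 | 20 | 30 |
|---|---|---|---|---|---|---|---|
| Simultaneous | 0 | 0.270 | 0.537 | 0.759 | 0.840 | 0.857 | 0.825 |
| Second-patch clock | 0 | 0.367 | 0.594 | 0.781 | 0.846 | 0.856 | 0.820 |

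The trapezoid gives 21.37 and 21.95, a ratio of 1.027. The 2-min sample is about 36% higher, but AUC0-30min rises by only 2.7%, because the interval from 0 to 2 min contributes little area and the later samples barely differ.

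**All 8 scenarios, relative to simultaneous application.**

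| Measure | g = 1 min | g = 2 min | g = 5 min |
|---|---|---|---|
| AUC0-30min, second-patch clock | +0.8 to +1.9% | +1.2 to +3.6% | +1.1 to +7.7% |
| AUC0-30min, first-patch clock | −2.0 to −1.2% | −4.0 to −2.7% | −10.2 to −8.0% |
| AUC0-60min, second-patch clock | +0.2 to +0.7% | +0.3 to +1.4% | −0.3 to +2.7% |
| 2-min sample | +11 to +22% | +18 to +41% | +26 to +89% |
| 5-min sample | +2 to +7% | +3 to +14% | +3 to +30% |

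AUC0-120min stays within about 1%. Cmax and AUC0-last fall by at most 1.4%.

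**Tmax.** Measured from the first patch, Tmax is later by exactly g; that restates the change of clock. Against simultaneous application, the sample holding Cmax changed in 0 of the 8 scenarios. In a finer sweep (Tmax 10 to 30 min by 0.25 min, half-life 90 to 180 min by 15 min, 567 cases) it changed in 39, 75 and 162 cases, that is 7%, 13% and 29%, for gaps of 1, 2 and 5 min.

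**Is the direction fixed?** With single-patch Tmax of 2 to 7 min and the same half-lives, the AUC0-30min ratio is 0.996 to 1.004, 0.992 to 1.005 and 0.981 to 1.002 for the three gaps. The effect is close to nil and can go against M207. The draws at 2 and 5 min mean that absorption this fast cannot be ruled out.

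**Against the permitted timing error.** In the 8 scenarios, a nominal 2-min sample drawn at 3 min is 23% to 43% higher, and one drawn at 1 min is 38% to 48% lower. That error has no fixed sign and actual draw times are recorded, but the 2-min value is imprecise in any case.

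**The case for a change.** The best case for acting is that the offset is systematic while the ±1 min draw window is not, that half the dose is involved, and that two time fields would cost almost nothing. Against a first-patch clock, the second-patch clock gives an AUC0-30min that is 2-4%, 4-8% and 10-20% higher at gaps of 1, 2 and 5 min, and a Tmax shorter by the whole gap. Nothing in the protocol bounds the gap.

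The facts stand: no section demands the first-patch time, and a 5-minute gap would be noticeable in the earliest samples. Three things limit what follows.

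- The first-patch clock is not the truth either. It charges M207 with time when only half the dose was on the skin, and on AUC0-30min it generally misses simultaneous dosing by more than the present clock does. A sensitivity table on that clock would gain nothing.
- An actual dosing time is an ordinary case-report-form or source-record item. The site's standard forms are not shown and may already hold both times, so loss of the information is conjecture.
- The shorter wordings in sections 6 and 10.4 do not contradict the definition. Section 6.3.1.2 states the origin under the heading of treatment administration, and an analyst reading section 10.4 would take time 0 from there.

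**Conclusion.** No change to the plan is called for. The second-patch clock is a defensible convention. It is stated explicitly in the Synopsis and section 6.3.1.2, and it matches the removal time in section 5.1. At gaps of 1 to 2 min its effect on AUC0-30min ranges from −0.8% to +3.6% across all the absorption speeds examined; at 5 min, from −1.9% to +7.7%. Total exposure and Cmax hardly change. A, B and C share the clock, so their comparison is hardly affected provided that opening a pouch (A) and a cup (B, C) leads to similar gaps.

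The comparison with the spray is descriptive (section 10.4), has no formal sample size calculation (section 10.1) and sets 3.8 mg against 2.5 mg, a nominal dose ratio of 1.52. A shift of a few percent in one partial AUC would not alter its reading. What remains is a detail of data capture that the site and analysts can settle in the usual way. This rests on the assumed one-compartment kinetics and on gaps of a few minutes at most; the protocol states neither.
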